7.4.3 Covariates

Patient characteristics at baseline will be assessed for Tio+Olo and LABA/LAMA/ICS user overall and stratified by history of exacerbation, circulating eosinophils, subgroups defined by both exacerbation and eosinophil levels.

We will identify and describe the following demographic characteristics as of the index date:

- Sex
- Age (years, as both a categorical and a continuous variable)
- Calendar year of cohort entry

Proprietary confidential information © 2019 Boehringer Ingelheim International GmbH or one or more of its affiliated companies

- Season of index date (winter, spring, summer, fall)
- US census region of residence
- Insurance type (e.g., Commercial, Medicare)

Additional characteristics will be defined during the 12-month pre-index baseline period:

- Number of previous COPD treatments
- Specific previous COPD treatments
 - LAMA monotherapy
 - LABA monotherapy
 - ICS monotherapy
 - LAMA/ICS combination therapy
 - LABA/ICS combination therapy
- Previous acute COPD exacerbation (measured both overall and in the 30 days prior to cohort entry), categorized as 0, 1, or 2+.
 - All exacerbations (Moderate+Severe)
 - ED visits or dispensings of inhaled corticosteroids/antibiotics (Moderate)
 - Hospitalizations (Severe)
- Use of other respiratory drugs in the 12-month pre-index period:
 - Short-acting beta-agonists
 - Anticholinergics
 - Methylxanthines
 - Muscarinic antagonists
 - Short-acting muscarinic antagonists
- Use of antibiotics for a respiratory condition (e.g., azithromycin)

Chronic comorbidities will be defined using diagnoses identified during all available data prior to the index date, and will include:

- Cardiovascular disease
- Charlson comorbidity index
- Diabetes
- Thyroid disease
- Renal failure
- Autoimmune disease
- Pneumonia
- Obesity*
- Alcohol use disorder*
- Tobacco use or cessation counselling*
- Cancer (excluding basal cell carcinoma)
- * We anticipate limited capture of lifestyle variables known to be risk factors and potential confounders, including obesity, smoking status and excessive alcohol consumption. Although we will describe them as identified in the HIRD, bias analyses to examine the extent to which residual confounding may impact results are also planned.

Additionally to the covariates defined above, we will use the high-dimensional approach to identify variables entering a time-conditional propensity score.

Boehringer Ingelheim	
Protocol for non-interventional studies based on existing data	
BI Study Number 1237-0094	

Proprietary confidential information © 2019 Boehringer Ingelheim International GmbH or one or more of its affiliated companies

Sub-populations will include patients with high or low circulating eosinophils (B-Eos 300 cells/uL [P18-09975] as identified based on the laboratory result value that is closest but prior to the index date (within 6 months). Additional stratification will include previous history of exacerbations in the year preceding cohort entry (with exacerbation history defined as either 1 + hospitalization or 2 + exacerbations in emergency department or outpatients settings), and among those without a history of exacerbation at baseline, based on circulating eosinophil results as noted above. However, number of patients with baseline exacerbations and data available on B-Eos is very low (see section 7.7) and therefore analysis would not be meaningful and will not be performed.

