7.4 VARIABLES

7.4.1 **Exposures**

The exposure measures are based on pharmacy dispensings of the study medications, namely Tio+Olo and LABA/LAMA/ICS combination therapy. As described in the data analysis section, the as-treated analysis, which is the main analysis, will consider continuing exposure of the initial treatment of Tio+Olo or LABA/LAMA/ICS within the treated groups defined by the days supply recorded at the time of pharmacy dispensing, allowing for a gap between dispensings of up to 15 days. This gap is allowed in consideration of plausible delays in obtaining medication refills and continued use beyond the days supplied where medication has been missed due to imperfect adherence, and will be varied in sensitivity analyses (see Section 7.9.2). Codes used to identify study medications are included in Annex 3.1.

The treatment segment ends at the earliest of the following events:

- 1. Fifteen days after the end of the observed days supply for the medication received on the index date without a subsequent dispensing of COPD medication (i.e., discontinuation)
- 2. Initiation of triple therapy (i.e., addition of ICS to Tio+Olo or a LAMA to LABA/ICS (i.e., treatment escalation, applies to Tio+Olo only)
- 3. Any other change in use of study medication by active ingredient, inclusive of a change to a different combination therapy, change from a fixed form to a free form combination therapy, or a change from combination therapy to monotherapy (i.e., switch)

Changes in dose for medications started on the index date will not impact the end of the treatment segment. Codes used to identify study medications are included in Annex 3.1.

7.4.2 **Outcome(s)**

7.4.2.1 **Primary outcome(S)**

The primary outcome event for effectiveness is the first COPD exacerbation to occur after cohort entry. The event is defined as follows:

- Severe exacerbation: •
 - Hospitalization with a principal discharge diagnosis of COPD.
 - Moderate exacerbation:
 - An ED visit with a discharge diagnosis of COPD and/or
 - Dispensing of an antibiotic and an oral corticosteroid on the same day

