7.6 BIAS

Several potential biases are inherent to any observational study in the HIRD. In the absence of randomization, confounding by indication could be an issue. Controlling by propensity score should limit this bias, but can control only for measured covariates and may produce estimates that are impacted by residual confounding. This is of particular importance in the case of lifestyle factors that are less critical to insurance billing and thus poorly captured in claims data. Quantitative bias analyses can formally describe the extent to which these issues are present, but bias analysis parameters are informed by literature and clinical expert opinion. As such, the accuracy of bias corrected analyses is limited by the accuracy of the assumptions that inform them [R19-3031].

Second, there is the possibility of information bias due to misclassification of the outcomes or exposure or missing data, especially, differential missingness of some data (e.g. eosinophils, which may only be measured in sicker patients). The prescriptions dispensed by a pharmacy but not taken by patients could lead to misclassification of exposure. Pharmacy dispensing data does bring us one step closer to patient use than physician prescribing given that the patient has taken the effort to obtain the medication as instructed, however, information such as indication can only be inferred based on diagnostic patterns.

Proprietary confidential information © 2019 Boehringer Ingelheim International GmbH or one or more of its affiliated companies

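### Oral corticosteroid courses, home oxygen, pulmonologist visits and baseline utilization and cost are not among the pre-specified covariates, so their adjustment and balance reporting depend on the data-derived step

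*Combined protocol and SAP*

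**What the plan says.** Section 7.4.3 pre-specifies these severity markers:

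- exacerbation history: "Previous acute COPD exacerbation (measured both overall and in the 30 days prior to cohort entry), categorized as 0, 1, or 2" (the top category is open-ended, 2+)
- moderate events: "ED visits or dispensings of inhaled corticosteroids/antibiotics (Moderate")
- severe events: "Hospitalizations (Severe")
- "Number of previous COPD treatments", and which ones
- short-acting beta-agonists, anticholinergics, methylxanthines and muscarinic antagonists, under "Use of other respiratory drugs in the 12-month pre-index period"
- respiratory antibiotics, pneumonia and the Charlson index

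The section then says that "we will use the high-dimensional approach to" find further variables. Section 7.9.1 confirms that the score combines the fixed and the data-derived variables. It treats a standardized difference above 0.10 as imbalance that calls for refinement. Section 7.6 concedes that the score "can control only for measured covariates and may produce estimates that are impacted by residual confounding".

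The fixed list has no oral corticosteroid courses, home oxygen, pulmonologist visits, or baseline all-cause visits and cost. Annex 3.3 shows no codes for any of them. Corticosteroid codes appear only in the outcome annex (3.2). Utilization and cost are planned only as an exploratory comparison (sections 6 and 7.9.1).

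**The concern.** No lung-function or symptom variable is listed, so claims proxies have to carry disease severity. The background describes recommendations to reserve triple therapy for patients likely to respond to ICS, such as those at high exacerbation risk with raised eosinophils. Some channelling of sicker patients to triple therapy is therefore plausible.

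An unlisted marker is adjusted for only if the data-derived step picks it up. If it is not picked up, it also need not appear among the patient characteristics checked for balance, and the 0.10 rule would not flag it. At stake is residual severity confounding in the exacerbation and pneumonia hazard ratios, and in the descriptive cost comparison if it is made in the weighted population.

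**Working it through.** **1. Is each marker already covered by another covariate?**

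- *Oral corticosteroids.* The covariate for moderate events refers to inhaled corticosteroids, whereas the outcome in 7.4.2.1 requires "Dispensing of an antibiotic and an oral corticosteroid on the same day". Used as written, the covariate does not capture oral steroids. If inhaled is a slip for oral, capture is partial. Under the outcome rule, a steroid-only course, or one dispensed on a different day from the antibiotic, would not count, and the count is capped at 2+.
- *COPD-specific utilization.* Partly covered by COPD hospitalizations and ED visits.
- *Home oxygen, pulmonologist visits, all-cause utilization and cost.* No listed covariate measures these.
- *Annex 3.3.* It is headed as complete, but its silence is not decisive. Pneumonia is a listed covariate and is coded only in Annex 3.2. The absence from 7.4.3 is what counts.

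**2. How far does exacerbation history separate patients?** Counts are from the table in section 7.7.

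| | Tio+Olo | Triple |
|---|---|---|
| Low history | 1,381 + 481 + 2,739 = 4,601 | 9,516 + 3,481 + 21,813 = 34,810 |
| High history | 226 + 105 + 537 = 868 | 1,888 + 707 + 4,822 = 7,417 |
| Total | 5,469 | 42,227 |

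The totals reproduce the table's COPD row. The low-history share is 4,601/5,469 = 84% and 34,810/42,227 = 82%. By definition these patients have no inpatient and at most one outpatient event, so the count covariate reduces to 0 versus 1. Three of the six strata in 7.9.1 lie wholly inside this group. Severity there has to come mainly from other markers.

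The crude high-history imbalance is 15.9% versus 17.6%. Standardized difference = (0.1756 − 0.1587) / √{[0.1587(0.8413) + 0.1756(0.8244)]/2} = 0.045.

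**3. How large could the bias be?** For a binary marker independent of the adjusted covariates, the spurious triple-versus-Tio+Olo ratio is

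[1 + p1(RR − 1)] / [1 + p0(RR − 1)],

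with p1 the prevalence on triple therapy and p0 the prevalence on Tio+Olo. All inputs are assumed; none is in the documents.

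- p1 = 15%, p0 = 10%, RR = 2: 1.15/1.10 = 1.045
- p1 = 20%, p0 = 12%, RR = 2.5: 1.30/1.18 = 1.10
- Wider range (p0 5–20%, p1 higher by 5–15 points, RR 1.5–3): 1.02 to 1.27
- Marker held at a standardized difference of 0.10 (p0 5%, 10%, 20% with p1 7.4%, 13.2%, 24.1%; RR 1.5–3): 1.01 to 1.06

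Section 7.7 uses a hazard ratio of 0.85 as its benchmark, and 1/0.85 = 1.18. A bias of that size needs a large gap, for example 5% versus 15% with RR 3: 1.30/1.10 = 1.18.

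**4. The plan's power figure.** The claim of over 90% power with 2,000 per cohort cannot be reproduced, because no event proportion is given. This point does not depend on it.

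**The case against.** The strongest reply is that severity is already well represented. Exacerbation history over two windows, COPD hospitalization, ED visits, prior treatments, relievers, respiratory antibiotics, pneumonia and the Charlson index are all fixed, and the high-dimensional step is added to them. That stands, and it rules out two readings that a reader might reach: that the plan omits the main claims markers of severity, and that control of severity is left to data-driven selection.

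Nor can the high-dimensional step be called unspecified. The contents page lists an Annex 3.4 on statistical considerations whose text was not available here, and the settings may be there. The documents also do not say how that step codes its variables, so no argument should rest on coding.

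A reader might further infer that the hazard ratio will be biased against triple therapy with no warning, or that the protocol calls confounding by indication its main threat. The documents support neither. Section 7.6 says only that such confounding could be an issue. Sections 7.6 and 7.11 disclose residual confounding, and bias analyses are planned, though they are introduced in the footnote on lifestyle variables. The only severity data given show little crude imbalance (0.045). Those counts do not show the asthma, other-lung-disease and prior-use exclusions, and they say nothing about oxygen or specialist care. They therefore neither establish channelling nor exclude it.

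The narrower fact is unanswered: the named markers are not on the list, and nothing in the available text requires that they be adjusted for or shown in the balance table.

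**Conclusion.** The point holds as a gap in an otherwise substantial covariate list. Oral corticosteroid courses, home oxygen, pulmonologist visits and baseline all-cause utilization and cost are not pre-specified, and the available text leaves their control and balance reporting to the data-derived step. The gap matters most in the low-history strata, which hold 84% and 82% of patients and where exacerbation counts separate little.

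The size and direction of any bias are unknown. The figure of 1.05–1.10 rests on assumed prevalences and risk ratios and on independence from the adjusted covariates; correlation with covariates already in the score would be expected to reduce it. It is smaller than the 15% benchmark but not negligible beside it. This is a worthwhile, low-cost improvement. It does not show that severity is uncontrolled.

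**What to change.** - Add to 7.4.3, over the 12-month baseline: number of oral corticosteroid courses, home oxygen claims, pulmonologist visits, and all-cause and COPD-specific visits and cost. Add the definitions and codes to Annex 3.3, or refer to Annex 3.2 where codes already exist.
- Force these into every propensity-score fit, overall and in the laboratory subset, and show them in the balance table before and after weighting. Section 7.9.1 repeats the stratification and reweighting in that subset but does not say explicitly that the score is re-estimated; state this.
- Keep the high-dimensional step on top. State its settings, or refer to Annex 3.4 if they are there.
- Reconcile the inhaled corticosteroid wording of the moderate-exacerbation covariate in 7.4.3 with the oral corticosteroid in 7.4.2.1.

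The cost is a few more covariates from claims already held, with slightly more model complexity in the laboratory subset (about 2,200 Tio+Olo users). The cohort sizes do not change.

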7.3 SUBJECTS

The study cohort will be formed based on the following entry criteria.

Inclusion Criteria:

- 1. At least one prescription for Tio+Olo or a LABA/LAMA/ICS combination between 1 January 2013 and 31 March 2019.
 - a. For Tio+Olo users, the first dispensing of Tio+Olo will be defined as the index date.
 - b. LABA/LAMA/ICS use can occur either in free or fixed combinations. The first date when all three medications are used based on either concurrent or overlapping dispensings in the pharmacy claims data will be defined as the index date.
- 2. At least one diagnosis of COPD at any time prior to the index date.
- 3. At least one year of continuous medical and pharmacy health plan eligibility prior to the index date will be required to allow a baseline period for the covariates and identification of new use of the study drugs.

Exclusion Criteria:

- 1. To increase the likelihood of a true diagnosis of COPD, we will exclude:
 - a. All patients less than 40 years of age on the index date, and
 - b. All patients with a diagnosis of asthma in the year prior to the index date
- 2. To limit the population to those without severe lung compromise outside of COPD, we will exclude individuals with lung cancer, interstitial lung disease, or lung transplant identified at any time prior to the index date
- 3. To restrict the cohort to new users of Tio+Olo or LABA/ICS, we will exclude any individual with use of either Tio+Olo, LABA/ICS, or LABA/LAMA/ICS combination therapy in free or fixed form for at least one year prior to the index date.

Outpatient laboratory data is available for a subset of patients. Some analyses will be further restricted to the subset of the population with at least one laboratory result showing circulating eosinophil levels within six months before the index date.

Individuals in the study cohort will be followed from the index date until the earliest of the date of a switch in treatment, addition of ICS for the Tio+Olo group, discontinuation of

COPD treatment, the end of the study period, or the end of continuous health plan eligibility. Main analyses will be further limited to the first year after cohort entry, with sensitivity analyses considering all available data.

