7.5 DATA SOURCES

This study will be conducted using the HIRD, a large administrative healthcare database maintained by HealthCore for use in health outcomes and pharmacoepidemiologic research. The HIRD includes longitudinal medical and pharmacy claims data from health plan members across the United States (US). Member enrolment, medical care (professional and facility claims), outpatient prescription drug use, outpatient laboratory test result data, and health care utilization may be tracked for health plan members in the database dating back to January 2006, and with diagnoses recorded in International Classification of Disease, Version 10 (ICD-10) since October, 2015. Laboratory result data are additionally available for those tests that have been performed using two large, national reference laboratories (Quest and LabCorp) [R14-4278]. The database has been used for the study of numerous diseases, including studies of COPD [R19-2324; R19-2321; R19-2323; R19-2322; P15-11025; P14-12233]

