7.7 STUDY SIZE

	Tio	+Olo	ICS/LABA	A/LAMA
	Ν	%	Ν	%
New users	8,233	100.0	82,534	100.0
At least 12 months of				
pre-index eligibility	6,263	76.1	50,153	60.8
Age 40 +	6,126	97.8	48,267	96.2
At least 1 diagnosis of COPD	5,469	89.3	42,227	87.5
At least 1 eosinophil % result				
prior to the index date	2,207	40.4	15,699	37.2
Eosinophil result (N, % of				
those with a result)				
0-2%	1,059	48.0	7,488	47.7
2-4%	745	33.8	5,136	32.7
4%+	403	18.3	3,075	19.6
Eosinophil result, patients				
with low exacerbation				
history(0 inpatient and 0-1				
outpatient events at baseline,				
N, %)				
<300 cells/uL	1,381	30.0	9,516	27.3
\geq 300 cells/uL	481	10.5	3,481	10.0
Unknown	2,739	59.5	21,813	62.7
Eosinophil result, patients				
with high exacerbation history				
(1 + inpatient or 2 + outpatien)				
t events at baseline, N, %)			vents	
<300 cells/uL	226	26.0	1,888	25.5
≥300 cells/uL	105	12.1	707	9.5
Unknown	537	61.9	4,822	65.0

Preliminary patient counts in the HIRD are shown here:

In a recent analysis of the risk of exacerbations based on Clinical Practice Research Datalink (CPRD), a total of 2,000 patients per cohort detected a 15% difference in risk of a first exacerbation (hazard ratio 0.85) with over 90% power. As such, overall analyses and analyses that are stratified based on the presence of claims-based indicators of exacerbation are expected to have adequate power. Analyses limited to individuals with specific eosinophils will be more limited. Given low expected sample size, stratification by eosinophil analysis within individuals with exacerbations at baseline will not be performed by Eosinophil categories.

7.8 **DATA MANAGEMENT**

All statistical analysis for the study will be conducted using SAS version 9.4 or higher (SAS Institute, Cary, NC). All sensitive data pertaining to the study will be stored on secured servers with access only permitted by approved study team members.

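### Comorbidities are measured over histories of 1 to about 13 years, but length of history is not a listed propensity-score covariate and no common-window analysis is stated

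*Combined protocol and SAP*

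**What the plan says.** Section 7.4.3 uses two measurement windows. For prior COPD treatments, exacerbations and respiratory drugs: "Additional characteristics will be defined during the 12-month pre-index baseline period". For the comorbidity block, which includes cardiovascular disease, the Charlson index, pneumonia, obesity, alcohol and tobacco: "Chronic comorbidities will be defined using diagnoses identified during all available data prior to the index date".

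Section 7.3 sets a minimum history and no maximum: "At least one year of continuous medical and pharmacy health plan eligibility prior to the index date will be required". Section 7.5 says that care "may be tracked for health plan members in the database dating back to January 2006". Index dates run from January 2013 to March 2019.

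The listed covariates include calendar year of cohort entry but not length of pre-index eligibility. Section 7.9.1 judges balance by standardized differences above 0.10 in patient characteristics. Sections 7.6 and 7.11 discuss residual confounding and poorly captured lifestyle factors, but not unequal length of history.

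The only enrolment figures by arm are in the section 7.7 table, in the row for at least 12 months of eligibility: "pre-index eligibility 6,263 76.1 50,153 60.8".

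**The concern.** A condition has more chances to be coded in ten years of claims than in one. With an open-ended window, the sensitivity of a recorded comorbidity depends on how long the patient has been enrolled. If one arm has longer histories, equally sick arms will look different, and the weighting will remove a difference in recording as though it were a difference in health. True disease is then pushed out of balance.

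The planned balance check cannot reveal this, because it compares recorded status only. Section 7.4.2.1 takes the same issue seriously for the outcome: it plans a comparison between groups to test whether outcome sensitivity is non-differential. No matching check is stated for covariates. At stake is residual confounding of the exacerbation and pneumonia hazard ratios behind a clean balance table.

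**Working it through.** **Range of history.** The minimum is 1 year. The maximum is about 7 years for an index date in January 2013 and about 13.2 years for one in March 2019, counting from January 2006.

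**The plan's own figures.** 6,263/8,233 = 76.1% and 50,153/82,534 = 60.8%; both reproduce. The difference is 15.3 percentage points (95% CI 14.3 to 16.3). The row removes 1,970 Tio+Olo and 32,381 triple users. Everyone retained has at least 12 months, so the row does not measure any difference in history that remains.

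**Illustration.** The documents give no history length for the analysed cohort, so everything below rests on assumptions.

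1. Constant enrolment turnover, extrapolated from the 12-month row. Yearly rates: λ = −ln(0.761) = 0.273 for Tio+Olo and −ln(0.608) = 0.498 for triple. History is 1 year plus an exponential time, with mean 1 + 1/λ = 4.7 and 3.0 years. A 10-year cap gives 4.3 and 3.0.
2. A true condition is coded in any year with probability c = 0.20, independently between years, with no false positives. Sensitivity = 1 − (1 − c)λ/(λ − ln(1 − c)).
   - Tio+Olo: 1 − 0.8 × 0.273/0.496 = 0.56
   - Triple: 1 − 0.8 × 0.498/0.721 = 0.45
3. True prevalence is equal in both arms, at 50% or 60%. Triple users are reweighted to the recorded prevalence of Tio+Olo; section 7.9.1 does not state the weighting target, so this is also assumed.

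| Step | True prevalence 50% | True prevalence 60% |
|---|---|---|
| Recorded, Tio+Olo vs triple | 0.280 vs 0.224 | 0.336 vs 0.269 |
| Standardized difference, recorded, before weighting | 0.13 | 0.15 |
| Truly diseased share of unrecorded triple users | 0.276/0.776 = 0.356 | 0.331/0.731 = 0.453 |
| True prevalence in triple after weighting | 0.280 + 0.720 × 0.356 = 0.536 | 0.336 + 0.664 × 0.453 = 0.637 |
| True imbalance after weighting | 3.6 points | 3.7 points |
| Standardized difference, true disease | 0.07 | 0.08 |

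4. Shift in the hazard ratio, triple relative to Tio+Olo, for a comorbidity with an assumed outcome rate ratio R: [1 + (R − 1) × 0.536]/[1 + (R − 1) × 0.5]. With R = 1.5 this is 1.268/1.25 = 1.014. With R = 3 it is 2.072/2 = 1.036.

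**Wider inputs.** With the 10-year cap, true prevalence of 10% to 50% and annual recording rates of 0.1 to 2, the standardized difference in recorded status before weighting is 0.004 to 0.12. The true imbalance after weighting is 0.1 to 3.6 points, and the hazard ratio shifts by a factor of 1.00 to 1.04. If history beyond 12 months is equal, all of these effects are zero.

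**Does the remedy work?** In a simulation of the scenario in steps 1 to 3, adding length of history to the propensity score restored true balance.

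**The case against.** The strongest reply is that the 76.1% and 60.8% describe the wrong population: apparent new users before the restriction. Patients already on triple therapy when they join the plan look new until a year of history is required, and identifying new use is a stated purpose of that requirement. If about 20% of triple users were such joiners (16,630 of 82,534), the remaining 65,904 would give 50,153/65,904 = 76.1%, and the whole gap would vanish with no difference in later history. That 20% is an assumption, but so is constant turnover, and the documents favour neither. This objection stands: unequal history in the analysed cohort is a possibility, not a documented fact.

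A reader might also infer that a standardized difference of 0.13 to 0.15 breaches the plan's 0.10 limit and so shows a confounded hazard ratio. It does not. That figure is the recorded difference before weighting; the true imbalance left afterwards is about 0.07 to 0.08 in the same scenario.

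Nor do the documents support saying that there is no adjustment at all. Calendar year of entry bounds the available history, and the score is called high-dimensional and time-conditional, although the text does not define the time it conditions on. Annex 3.4 is listed in the contents but is not in the text available, so its content cannot be judged. Bias analyses are planned for obesity, smoking and alcohol. These points help only in part: patients entering in the same year can have very different histories, and the bias analyses are described for limited capture, not for capture that differs by arm.

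Finally, adjusting for length is not guaranteed to restore balance, because what an unrecorded condition means depends on length of history. It did so in the scenario tested; a flexible form is the sensible safeguard.

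**Conclusion.** The point holds as a gap in the covariate plan, not as a demonstrated bias. The comorbidity window is open-ended, length of history is not a listed covariate, no common-window analysis appears in the available text, and the balance check cannot detect unequal recording opportunity. Covariates with the fixed 12-month window are unaffected.

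The size is modest and conditional. Under constant turnover and the inputs above, true imbalance in one comorbidity is up to about 3.7 percentage points and the hazard ratio shifts by at most about 4%. If Tio+Olo has the longer histories, the shift raises the triple-versus-Tio+Olo hazard ratio; if triple does, it reverses. Several affected comorbidities could add up. If history is equal, there is no effect. Only the sponsor can see which case applies, and the plan does not commit to looking. This is an inexpensive improvement worth making.

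**What to change.** In section 7.4.3:

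1. Report days of continuous pre-index eligibility by arm in the analysed cohort.
2. Add this length to the pre-specified propensity-score variables and to the balance table, in a flexible form such as categories or a quadratic.
3. Repeat the primary analysis with comorbidities restricted to the 12-month baseline that every patient has, keeping the all-available definition as primary.

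Section 7.3 already requires eligibility to be determined, so no new data source is needed. The cost is one covariate and one sensitivity run. The 12-month run captures less comorbidity information, so it should be read as a comparison with the main result, not as a better estimate.
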